### 5.7 Longitudinal safety and tolerability phase (44 weeks)

This is a continuation of the study beyond the initial 20-week intervention to continue to assess participants who chose to continue with TIL-TC150 therapy beyond the primary analysis period.

Week 28: Participant to return for clinical evaluation (including physical and neurological examination) as they have decided to continue TIL-TC150. Their dose will be 16mg/kg/day CBD divided twice daily or their individual maximally tolerated dose during

the intervention period. Their seizure diary will be reviewed. The Pediatric Epilepsy Side Effect Questionnaire (PESQ) will be completed to assess for any adverse events and tolerability and QOLCE completed by caregiver/parent.

Week 40: Participant to return for clinical evaluation (including physical and neurological examination) and seizure diary reviewed. The Pediatric Epilepsy Side Effect Questionnaire (PESQ) will be completed by participant parent/legal guardian to assess for any adverse events and tolerability. Bloodwork will be performed once to check CBC, LFT, and Renal profile and trough AED levels during weeks 40-64.

Week 52: Participant to return for clinical evaluation (including physical and neurological examination) and seizure diary reviewed. The Pediatric Epilepsy Side Effect Questionnaire (PESQ) will be completed by participant parent/ legal guardian to assess for any adverse events and tolerability and QOLCE completed by caregiver/parent. Bloodwork will be performed to check CBC, LFT, and Renal profile and trough AED levels. If the blood work is done at week 40, then no need to repeat.

Week 64: Participant to return for clinical evaluation (including physical and neurological examination) and seizure diary reviewed. The Pediatric Epilepsy Side Effect Questionnaire (PESQ) will be completed to assess for any adverse events and tolerability by caregiver/parent. For families who choose to continue therapy for the longer term, they will be invited to complete a Vineland assessment during 52-64 weeks by the psychology team in our study to measure any changes in behaviour. Bloodwork will be performed to check CBC, LFT, and Renal profile and trough AED levels. If the blood work is done at week 40 or 52, then no need to repeat.

After this time point participants will resume care with their regular pediatric neurologist. Written communication regarding their therapy and current dosing will be forwarded by the study investigators to this physician. In addition, the study team will be available by telephone or email to provide support to physicians as participants' transition back to their care; in particular should they have any questions about TIL-TC150.

For the weeks of the study that the participants are not being evaluated in person at The Hospital for Sick Children, follow-up emails and/or phone calls will be made. This communication will occur in between the clinical visits for the intervention period - week 1, 3, 5, 6, 7, 10, 14, and 18. Participant's parent/ legal guardian will be asked about their child's dosage to ensure correct titration or if already at maximal study protocol dose (as determined during the intervention period) how they are tolerating it. Adverse events and concomitant medications will always be assessed and any concerns participant, parent/caregiver may have will be addressed.

The study participant will be given a window of +/- 3 days around the timing of each study visit during the intervention period and +/- 14 days for the post-intervention longitudinal visit scheduling.

5.8 Schedule of Events table:

| Study Period             | Week # | Participant/ study team interaction   | TIL-TC150Dose   |
|---------------------------------|---------------|--|--|
| Pre- Intervention Period | -4            | Clinic visit – education, baseline physical and neurological review and urine test for THC for those only who have not been on cannabinoids for at least last 60 days.                                       | None   |
| Baseline analysis        | -4 to 0       | Participant parent/legal guardian completion of seizure diary; 24 hour ambulatory EEG, psychologist will arrange for parent/caregiver to complete a Vineland assessment                                      | None   |
| Intervention period      | 0             | Clinic visit – education, weight, physical and neurological review; baseline bloodwork; collection of baseline seizure diary; education regarding dosing of study product; parent to complete baseline QOLCE | Starting at 2mg/kg/day CBD divided in 2 equal doses; first dose given in clinic with 2 hours of observation post-dose. |
|                                 | 1             | Telephone and/ or email contact by study team to determine dosing and tolerability   | Once tolerance ensured, increase dose to 4mg/kg/day CBD divided twice daily  |

|    |  |   |
|----|--|---|
| 2  | Clinic visit – tolerance review, adverse events,; physical and neurological exam; parent/legal guardian to complete PESQ; seizure diary review   | Once tolerance ensured, increase to 6mg/kg/day CBD divided twice daily  |
| 3  | Telephone and/ or email contact by study team to determine dosing and tolerability   | Once tolerance ensured, increase to 8mg/kg/day CBD divided twice daily  |
| 4  | Clinic visit – tolerance review, adverse events; physical and neurological exam; parent/legal guardian to complete PESQ; seizure diary review; bloodwork   | Once tolerance ensured, increase to 10mg/kg/day CBD divided twice daily |
| 5  | Telephone and/ or email contact by study team to determine dosing and tolerability   | Once tolerance ensured, increase to 12mg/kg/day CBD divided twice daily |
| 6  | Telephone and/ or email contact by study team to determine dosing and tolerability   | Once tolerance ensured, increase to 14mg/kg/day CBD divided twice daily |
| 7  | Telephone and/ or email contact by study team to determine dosing and tolerability   | Once tolerance ensured, increase to 16mg/kg/day CBD divided twice daily |
| 8  | Clinic visit – tolerance review, adverse events; physical and neurological exam; parent/legal guardian to complete PESQ and QOLCE; seizure diary review; bloodwork performed once child is at target / maximal tolerated dose (any stage from week 8-16) | If tolerated, dose to continue at 16mg/kg/day CBD divided twice daily   |
| 10 | Telephone and/ or email contact by study team to determine dosing and tolerability   | If tolerated, dose to continue at 16mg/kg/day CBD divided twice daily   |
| 12 | Clinic visit – tolerance review, adverse events; physical and neurological exam; parent/legal guardian to complete PESQ; seizure diary review; bloodwork performed once at target / maximal tolerated dose (if not done previously)                      | If tolerated, dose to continue at 16mg/kg/day CBD divided twice daily   |
| 14 | Telephone and/ or email contact by study team to determine dosing and tolerability   | If tolerated, dose to continue at 16mg/kg/day CBD divided twice daily   |

|                                      |       |  |   |
|--------------------------------------|-------|--|---|
|                                      | 16    | Clinic visit – tolerance review, adverse events; physical and neurological exam; parent/legal guardian to complete PESQ and QOLCE; seizure diary review; bloodwork performed once at target / maximal tolerated dose (if not done previously)  | If tolerated, dose to continue at 16mg/kg/day CBD divided twice daily   |
| Primary Analysis              | 16-20 | Telephone and/ or email contact by study team at 18 weeks to determine dosing and tolerability

Psychologist will arrange for parent/caregiver to complete a Vineland assessment

Participant parent/legal guardian completion of seizure diary during this 4 weeks; 24 hour ambulatory EEG. Collection of seizure diary reported seizure frequency. | If tolerated, dose to continue at 16mg/kg/day CBD divided twice daily   |
|                                      | 20    | If tolerated, and participant parent/legal guardian wishes to continue study product dose to continue at 16mg/kg/day CBD divided twice daily   |   |
| Longitudinal follow-up period | 28    | Clinic visit – tolerance review; physical and neurological exam; parent/legal guardian to complete PESQ and QOLCE; seizure diary review;   | If tolerated, and participant parent/legal guardian wishes to continue, dose to continue at 16mg/kg/day CBD divided twice daily |
|                                      | 40    | Clinic visit – tolerance review; physical and neurological exam; parent/legal guardian to complete PESQ; seizure diary review;

Follow up bloodwork performed once (any stage from week 40-64)   | If tolerated, and participant parent/legal guardian wishes to continue, dose to continue at 16mg/kg/day CBD divided twice daily |
|                                      | 52    | Clinic visit – tolerance review; physical and neurological exam; parent/legal guardian to complete PESQ and QOLCE; seizure diary review;

Follow up blood work performed once (if not done previously)

During 52-64 weeks psychologist will arrange for parent/caregiver to complete a Vineland   | If tolerated, and participant parent/legal guardian wishes to continue, dose to continue at 16mg/kg/day CBD divided twice daily |

|  |    |   |   |
|--|----|---|---|
|  |    | assessment  |   |
|  | 64 | Clinic visit – tolerance review; physical and neurological exam; parent/legal guardian to complete PESQ; seizure diary review

Follow up blood work performed once (if not done previously) | If tolerated, and participant parent/legal guardian wishes to continue, dose to continue at 16mg/kg/day CBD divided twice daily |

NB\* At all periods during the study there will be study personnel available 24 hours through the main hospital switch board by telephone pager system for participant, parent/legal guardian should they have any concerns or queries out of hours or outside of these contact times.

**NB Should clinical concern arise during reviews about potential toxicity (clinical evidence of accentuated AED action such as somnolence, change in mentation etc), a further blood draw may be performed to evaluate trough AED level (for AED where trough routinely assessed).**

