## Study Summary

|                                       |  |
|---------------------------------------|--|
| Title                                 | Cannabinoid Therapy in Medically Refractory Pediatric Epilepsy – Phase 1: Dosing and Tolerability Study of a Cannabidiol-Rich Whole Plant Extract of Cannabis.   |
| Short Title                           | Cannabinoid Therapy for Pediatric Epilepsy   |
| Phase                                 | 1  |
| Methodology                           | Open-label Intervention  |
| Study Duration                        | 20 weeks to primary analysis with continued follow-up until 64 weeks completed   |
| Study Center                          | The Hospital for Sick Children, Toronto Ontario  |
| Objectives                            | To determine the tolerability and optimal dose of 50:1 ratio CBD:THC Cannabis extract as an adjunct treatment in children with severe drug resistant epilepsy  |
| Number of Subjects                    | 20   |
| Diagnosis and Main Inclusion Criteria | Patients with Dravet Syndrome

Between ages of 1 and 18 years old male or female

Must have failed 2 AEDs at therapeutic doses and be on current regimen of 1-4 AEDs which have been stable doses for 4 weeks  |
| Study Product, Dose, Route, Regimen   | TIL-TC150 Oil is the study product
The active ingredients in TIL-TC150 Oil are THC and CBD, present in a 1:50 ratio. These active ingredients are derived from Cannabis sativa L. strains produced by Tilray and suspended in a grape seed oil. This suspension is administered at a dose of 2mg/kg/day CBD divided BID and titrated up to a maximal dose of 16mg/kg/day CBD (or maximal tolerated). |
| Duration of Administration            | Study period: primary safety and outcome data at 20 weeks with longer follow-up of safety and tolerability in those who chose to continue after the 20-week period and will be followed up to 64 weeks.  |
| Reference Therapy                     | None   |
| Statistical methodology               | The primary aims of this study are to determine the maximal tolerated dose of TIL-TC150 Oil Cannabis Extract in children with drug resistant epilepsies. Descriptive statistics will be used to quantify the frequency and severity of adverse events that are   |

|  |  |
|--|--|
|  | reported for the various dosages that are employed |
|--|--|

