### 3.3 Longitudinal safety and tolerability (44 weeks)

For those participants who chose to continue TIL-TC150 therapy after the initial intervention period, they will be followed by the investigator team in clinic at 3 monthly intervals to assess for any tolerability and safety issues that arise with more prolonged therapy. They will be followed to 64 weeks.

Once the participant is stable on the therapy the frequency of visits and phone calls may be reduced at the discretion of the investigator team in conjunction with discussion with participant family.

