### 5.2 Treatment Regimen

Each participant will start the treatment with a dose of 2mg/kg/day CBD given in two equal doses each day. The first dose will be given during the Baseline (Week 0) visit. Following this dose the participant will be observed by study personnel for a period of 2 hours. The participant's parent/legal guardian will increase the participant's dose by 2mg/kg/day CBD every 7 days as tolerated, to a maximal dose of 16mg/kg/day CBD. Once optimal dose is determined for each participant they may continue the treatment for the duration of study follow-up and thereafter it will be continued if wished by participants.

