## 7.2 Methods of assessing

During the intervention period and follow-up there will be regular clinic review and telephone/email evaluation of the participant to assess tolerability of the study treatment and screen for any adverse events. This will be done by direct questioning of participant, parent/caregiver at each review. In addition the study team will perform a physical and neurological examination of participant at each clinic review. Every clinic visit we will ask parent/ caregiver to complete a side effect questionnaire (PESQ questionnaire) and study team will review the daily seizure diary. In addition at regular

intervals during the study the participant will have bloodwork to evaluate hematopoiesis, liver and renal function and trough AED levels.

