## **8. Statistics**

### **8.1 Statistical Method**

This is an observational study. The primary aims of this study are to determine the tolerability of the study treatment in a cohort of children with medication resistant epilepsy due to Dravet syndrome. As such, there are no formal statistical methods required, rather descriptive statistics will be presented to quantify dosing tolerability and frequency of adverse events. All participants will be analyzed regardless of dose achieved or duration of study completed, according to intention to treat analysis. The study data will be entered into the REDCap database for analysis.

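### Adverse-event frequency by dosage has no defined measure, although both exposure time and how often families are asked differ by dose and study period

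*Combined protocol and SAP*

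**What the plan says.** **Analysis.** The Study Summary states: "Descriptive statistics will be used to quantify the frequency and severity of adverse events that are" "reported for the various dosages that are employed" (one sentence, split across table cells). Section 8.1 adds only that "descriptive statistics will be presented to quantify dosing tolerability and frequency of adverse events". Neither says whether frequency means events, children with an event, or a rate. Neither gives a rule for assigning an event to a dose, or mentions exposure time or contact spacing.

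**How events are found.** Sections 7.2 and 7.3 rely on direct questioning at each review and evaluation at each contact. For calls and emails, section 5.7 states: "Adverse events and concomitant medications will always be assessed". The daily diary (sections 5.5 and 6.2) covers seizures, status epilepticus, rescue medication and emergency or hospital attendance. It has no side-effect entry.

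**When families are asked.** Section 5.7 on calls and emails: "This communication will occur in between the clinical visits for the intervention period - week 1, 3, 5, 6, 7, 10, 14, and 18". Clinic visits after the first dose fall at Weeks 2, 4, 8, 12, 16, 28, 40, 52 and 64 (sections 5.6 to 5.8). For children who continue after Week 20, section 3.3 says "they will be followed by the investigator team in clinic at 3 monthly intervals to assess for any tolerability and safety issues". Section 7.2, however, says: "During the intervention period and follow-up there will be regular clinic review and telephone/email evaluation of the participant".

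**Dose.** Under section 5.2 the parent is to "increase the participant's dose by 2mg/kg/day CBD every 7 days as tolerated, to a maximal dose of 16mg/kg/day CBD". In the section 5.8 table, 16 mg/kg/day starts at Week 7.

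**The concern.** Tolerability by dose is the trial's main question, and section 3.3 uses the period after Week 20 to judge more prolonged therapy. On the planned schedule the top dose differs from every lower dose in two ways unrelated to pharmacology: it is taken for far longer, and for most of that time families are asked less often. The first raises any count. The second can lower any rate, because short, mild events such as somnolence, fatigue or gastrointestinal upset are the easiest to forget before the next contact. A by-dosage table that handles neither cannot be read as a dose effect, and a low long-term rate could not be separated from less frequent questioning.

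**Working it through.** The plan states no adverse-event rate, so there is no figure to reproduce. The contact calendar can be rebuilt.

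**1. Contacts.** Calls at Weeks 1, 3, 5, 6, 7, 10, 14 and 18 plus the clinic visits give Weeks 1 to 8 weekly, then 10, 12, 14, 16, 18, 28, 40, 52 and 64. The gaps after Week 18 are 10, 12, 12 and 12 weeks.

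**2. Exposure and contacts for a child on the section 5.8 schedule.**

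| Dose and period | Weeks | Listed contacts | Contacts per week |
|---|---|---|---|
| Each of 2, 4, 6, 8, 10, 12, 14 mg/kg/day | 1 | 1 | 1.00 |
| 16 mg/kg/day, Weeks 7–20 | 13 | 6 | 6/13 = 0.46 |
| Continued, Weeks 20–64 | 44 | 4 | 4/44 = 0.09 |

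Section 3.2 places the last increase at Week 8, and the Week 8 text in section 5.6 also describes an increase. On that reading 16 mg/kg/day has 5 contacts in 12 weeks to Week 20 (5/12 = 0.42), and the conclusion is the same.

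**3. Counts and percentages.** Assume a constant true rate of 0.1 events per week at every dose, 20 children and full recall. Expected events = 20 × 0.1 × weeks; percentage of children with an event = 1 − exp(−0.1 × weeks).

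- Each lower dose (1 week): 2.0 events; 9.5%.
- 16 mg/kg/day to Week 20 (13 weeks): 26.0 events; 72.7%.
- 16 mg/kg/day to Week 64 (57 weeks, all continuing): 114 events; 99.7%.

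The true rate is identical throughout; the contrast comes from exposure alone.

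**4. Person-time rate.** Assume that an event t weeks before the next contact is captured with probability exp(−t/τ). For a gap of g weeks between contacts, the captured share is (τ/g)(1 − exp(−g/τ)). With τ = 2 and g = 1 this is 2 × (1 − exp(−0.5)) = 0.79. Averaging over each period, with Weeks 18–20 waiting until Week 28:

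| τ (weeks) | 2–14 mg/kg/day | 16 mg/kg/day to Week 20 | Weeks 20–64 | Ratios to 2–14 mg/kg/day |
|---|---|---|---|---|
| 2 | 0.79 | 0.55 | 0.18 | 0.70; 0.23 |
| 4 | 0.88 | 0.69 | 0.34 | 0.78; 0.38 |
| 8 | 0.94 | 0.80 | 0.54 | 0.85; 0.57 |
| 26 | 0.98 | 0.92 | 0.81 | 0.94; 0.83 |
| Full recall | 1.00 | 1.00 | 1.00 | 1.00; 1.00 |

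The model and τ are assumptions; the documents give neither. The ratios do not depend on the true rate.

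**5. Dose or study week?** Contact spacing follows study week. A child held at 8 mg/kg/day from Week 3 has contacts at Weeks 4 to 8, 10, 12, 14, 16 and 18: 10 in 17 weeks to Week 20, or 0.59 per week. The contrast in step 2 therefore applies to children titrated on schedule.

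**6. Questionnaire.** The side-effect questionnaire (PESQ) is completed at clinic visits only. On schedule it falls at the end of the 4 mg/kg/day week (Week 2), at the end of the 8 mg/kg/day week (Week 4) and then on 16 mg/kg/day. It never falls on 2, 6, 10, 12 or 14 mg/kg/day, and no baseline PESQ is listed.

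**The case against.** A reader might infer that adverse-event frequency must fall with dose and time by construction. The documents do not support that. Contact is flat across the seven doses from 2 to 14 mg/kg/day. The plan names no person-time rate, and on the ordinary readings of frequency, counts or percentages, the figure at 16 mg/kg/day would be higher (step 3). A fall needs both a person-time rate and imperfect recall.

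Under-collection is also not certain. Section 7.1 sets a continuous reporting period and immediate evaluation of suspected events, and the note to section 5.8 provides a 24-hour pager. These stand as safeguards, chiefly for serious events, but both rely on the family volunteering a mild complaint.

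The 4 contacts in 44 weeks are the listed minimum. Section 7.2 extends telephone and email evaluation to follow-up, and section 3.3 mentions reducing phone calls, which presupposes some. That objection stands, but no such call is scheduled. Section 3.3 also lets contacts be thinned once a child is stable, so questioning could depend on apparent tolerability. Around Week 20, EEG, Vineland and diary collection bring further dealings with the family, although no adverse-event contact is listed after Week 18.

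Finally, the study is small and descriptive, and every scheduled increase has a tolerance check. Each child's titration decision does not depend on comparing rates between periods, so the point is limited to the by-dosage summary and the long-term tolerability statement.

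**Conclusion.** The concern holds in this form: exposure and ascertainment both differ by dose and period, and the plan handles neither. Counts and percentages would be inflated at 16 mg/kg/day, where on-schedule exposure is 13 weeks to Week 20 and 57 to Week 64, against one week at each lower dose. A person-time rate removes that distortion but leaves the second. Under the assumed recall model, with τ from 2 to 26 weeks, the recorded rate would be 0.70 to 0.94 of the lower-dose rate at 16 mg/kg/day to Week 20, and 0.23 to 0.83 in Weeks 20 to 64. With full recall both ratios are 1.

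The calendar is firm for on-schedule children to Week 18; after that it depends on whether unlisted calls are made. Serious events are least affected. The direction of bias depends on the measure chosen, which is why the measure must be fixed beforehand. This should be corrected, but it does not invalidate the study.

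**What to change.** 1. **Collection.** Add one daily line to the seizure diary that parents already keep: side effect present or absent, and which. Collection then no longer depends on contact spacing. The cost is slightly more parent burden over as long as 64 weeks, and it helps only weeks not yet recorded.
2. **Analysis.** In section 8.1 and the Study Summary, define the measure as events per person-week by dose at onset. Tabulate titration, post-titration to Week 20, and Weeks 20 to 64 separately, showing person-time and number of contacts. State that differences in contact-elicited events between periods will not be read as effects of dose or duration. Use serious events and events leading to dose change or withdrawal for cross-period comparison. Do not rely on the PESQ to compare doses, given where it falls. This costs wording only, provided onset date and dose at onset are recorded.
3. **Reconcile.** Sections 3.3, 5.7 and 7.2 must agree on whether calls continue after Week 18. Sections 3.2, 5.6 and 5.8 must agree on the week of the last scheduled increase.

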#### 4.4.2 Data Collection

For all participants who withdraw from the study we will invite them to attend a clinic evaluation within 4 weeks of withdrawal +/- 2 weeks. During this visit we will document: their dose reached, reasons for withdrawal, adverse events, seizure diary and PESQ will be assessed, patients will have a physical and neurological examination and AED trough levels and routine bloodwork (CBC, LFT, Renal profile).

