### 5.5 Pre-Intervention Period (4 weeks)

Once enrolled, the pre-intervention period begins. Participants will be seen and baseline physical and neurological examination performed. Medical information regarding seizures, medications, birth and development will also be collected. Participant parent / legal guardian will be instructed to keep a daily seizure diary for the next four weeks which will be used as a measure of baseline seizure frequency. Seizure diary will be kept by participant's parent/ legal guardian for the duration of the study follow-up period also. Seizure frequency for each seizure type will be recorded at baseline. Seizure types will be classified prior to study entry.

- A. Diary: Seizure frequency and type will be monitored and recorded in a participant's daily diary. Participant's parent/caregiver will report the seizure frequency, type, number of episodes of Status Epilepticus, use of rescue medication and attendance to ER/ hospitalizations.
- B. Prolonged EEG study: During the pre-intervention period each participant will have a 24 hour ambulatory EEG recording performed to enable objective measurement of a 24 hour sample of electrographic activity – ictal and interictal, which will be reported by a certified experienced Clinical Neurophysiologist who is not part of the investigator team.
- C. Vineland Adaptive Behaviour Scale, Second Edition: this is a standardized parent interview that will take 20-60 minutes to complete either in person at the clinic or by telephone prior to starting the TIL-TC150. The interview will also be completed again at the primary evaluation period (week 16-20) and again during the longitudinal follow-up (52-64 weeks). This will be done by a clinical research assistant, under supervision of a clinical neuropsychologist (Dr. [name], CPsych). Parents will be provided with a research report detailing the assessment findings at study completion.

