#### 5.6 Intervention Period – and Primary Evaluation (20 weeks)

Week 0: (Baseline): A neurological and physical exam (including measurement of vital signs) will be performed and the participant will be weighed. The parent / legal guardian will complete the QOLCE. During this visit their seizure diary will be evaluated and bloodwork will be performed for baseline measures (Complete blood count, LFT (AST ALT, gamma GT, bilirubin), renal profile (electrolytes, creatinine and urea), and AED trough levels). The participant's parent/legal guardian will be instructed on dosing and twice daily administration of TIL-TC150. Each participant will start TIL-TC150 at an initial dose of 2mg/kg/day CBD in 2 equally divided doses, this will be added to their current anti-epileptic drug therapy regimen. They will be advised to increase the dose of the study treatment after 7 days by 2mg/kg/day CBD. The study pharmacist will be present

at the first clinic visit to review dosing schedule, administration and pharmacy dispensing procedures. In addition study pharmacist will be available during the study period to provide education and support to families. The first dose will be administered in clinic and the participant will be observed for a period of 2 hours by study personnel to evaluate for any adverse events.

Week 2: Participant to return to The Hospital for Sick Children. Study treatment increased as tolerated by 2mg/kg/day CBD, neurological and physical exam will be performed and the participant will be weighed, and seizure diary evaluated. Medical history including concomitant medications will be reviewed. The Pediatric Epilepsy Side Effect Questionnaire (PESQ) will be completed by participant's parent/legal guardian to assess for any adverse events and tolerability.

Week 4: Participant to return to The Hospital for Sick Children. Study treatment increased as tolerated by 2mg/kg/day CBD, neurological and physical examination will be performed, weight recorded, seizure diary evaluated. Bloodwork performed (CBC, LFT, Renal profile, AED trough levels). Medical history including concomitant medications will be reviewed. The Pediatric Epilepsy Side Effect Questionnaire (PESQ) will be completed by participant's parent/ legal guardian to assess for any adverse events and tolerability.

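### A pre-dose PESQ is not assured: Section 7.2 asks for the questionnaire at all clinic visits, but the Week 0 entries in Sections 5.6 and 5.8 leave it out

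*Combined protocol and SAP*

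**What the plan says.** Section 2 measures dosing safety and tolerability by bloodwork, AED levels, parent or caregiver report, physician assessment, caregiver-reported tolerability and PESQ.

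Section 7.2 sets the frequency: "Every clinic visit we will ask parent/ caregiver to complete a side effect questionnaire". It opens with its scope: "During the intervention period and follow-up there will be regular clinic review".

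The visit entries differ at the start of treatment:

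- **Week -4 (Sections 5.5 and 5.8).** No PESQ is listed. On history, Section 5.5 says: "Medical information regarding seizures, medications, birth and development will also be collected".
- **Week 0 (Section 5.6).** The questionnaire named is the quality-of-life one: "The parent / legal guardian will complete the QOLCE. During this visit their seizure diary will be evaluated". The first dose is given in clinic at this visit, with two hours of observation.
- **Week 0 (Section 5.8).** The row lists "collection of baseline seizure diary; education regarding dosing of study product; parent to complete baseline QOLCE". PESQ is absent.
- **Week 1 (Section 5.8).** A dose step is scheduled: "Once tolerance ensured, increase dose to 4mg/kg/day CBD divided twice daily".
- **Week 2 (Section 5.8).** PESQ appears for the first time: "physical and neurological exam; parent/legal guardian to complete PESQ; seizure diary review".

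Section 4.4.2 adds a PESQ at the visit offered to children who withdraw: "adverse events, seizure diary and PESQ will be assessed".

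**The concern.** Under Section 7.1 a symptom is an adverse event if it is new or has become more severe during the study. That judgement needs the state before the first dose. There is no reference therapy, so each child is their own only comparator. Section 5.3 (Concomitant treatments) expects each child to be on one to four AEDs, which cause side effects of their own. Section 1.7.1 also warns that CBD may raise the levels of those drugs.

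Without a pre-dose PESQ, a symptom ticked at Week 2 cannot be compared with the same item before treatment. A symptom already present may be counted as treatment-emergent, or an early worsening may be missed. Either error would pass into the descriptive summaries of adverse events and tolerability planned in the Study Summary and Section 8.1. A pre-dose response that was not collected cannot be recovered later.

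**Working it through.** The plan gives no figure to reproduce. The check sets the Section 7.2 rule against each scheduled clinic visit.

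**1. Count of visits (Sections 5.5 to 5.8).**

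| Clinic visit (week) | PESQ listed? |
|---|---|
| -4 | No |
| 0 (first dose) | No |
| 2, 4, 8, 12, 16 | Yes (5 visits) |
| 28, 40, 52, 64 | Yes (4 visits) |

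- From Week 0: 1 + 5 + 4 = 10 visits, with PESQ at 5 + 4 = 9. Week 0 is the only omission.
- Including Week -4: PESQ at 9 of 11. The two visits without it are the only two that could give a pre-dose value.
- Listed pre-dose PESQs: 0.

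**2. Two readings of Section 7.2.**

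- *Literal.* Sections 5.6 and 5.8 both place Week 0 in the intervention period, and it is a clinic visit. Section 7.2 then requires a Week 0 PESQ, which both Week 0 entries omit. Section 7.2 also does not say whether it comes before or after the dose given at that visit.
- *On-treatment only.* The contradiction goes, but no pre-dose PESQ is planned at all.

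Neither reading secures a pre-dose response.

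**3. Position of the first listed PESQ.** Week 2 is day 14, and Section 5.7 allows ±3 days in the intervention period: 14 - 3 = 11 to 14 + 3 = 17. With steps of 2 mg/kg/day CBD every 7 days as tolerated (Section 5.2), the dose at that PESQ is:

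- on schedule: 2 + 2 = 4 mg/kg/day, and 4/16 = 25% of the protocol maximum;
- Week 1 step not tolerated: 2 mg/kg/day, and 2/16 = 12.5%;
- day-14 step taken at home before a visit on days 15 to 17: 6 mg/kg/day, and 6/16 = 37.5%. This case rests on Section 5.2 alone, because Sections 5.6 and 5.8 tie that step to the Week 2 visit.

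These figures show how far dosing has gone. They do not measure misclassification.

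**4. Comparison with the other repeated measures.** The seizure diary, ambulatory EEG, Vineland, QOLCE, bloodwork, AED levels, weight and examination all have a value from before treatment (Sections 5.5, 5.6 and 5.8). The two questionnaires that serve secondary aims, QOLCE and Vineland, have a baseline. PESQ, named under the primary objective, does not.

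**5. Overlap of symptoms.** Section 1.7.1 lists 21 possible reactions to the study product, counting the taste item and the hot or cold flashes item once each. Five also appear by name in the Section 1.2 list for AEDs and/or high-THC cannabis: dizziness, fatigue, somnolence, loss of appetite and falls. That is 5 of 21, or 6 of 21 if gastrointestinal disturbance is matched to the gastrointestinal heading. The second list mixes two sources, so the overlap shows that attribution is hard. It does not show what these children have before dosing.

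**6. Early withdrawal.** For a child who stops before Week 2, the PESQ at the withdrawal visit would be the only one.

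**The case against.** The strongest reply is that PESQ is an on-treatment tool. Section 7.2 is about tolerability of the study treatment, the PESQ entries in Sections 5.6 and 5.7 give adverse events and tolerability as their purpose, and the reporting period in Section 7.1 opens when treatment starts. On that reading the schedule is consistent. This is a fair reading, but it means that a pre-dose PESQ is not planned at all.

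A second reply is that no planned result depends on a baseline PESQ. The primary endpoint in Section 3.4 is the maximal safely tolerated dose, the analysis is descriptive, and no PESQ score or change score is specified. Whether an event is new or worse is a clinical judgement by a team that examines the child at Weeks -4 and 0 and asks about adverse events at each contact, including the Week 1 call. AED doses must also be stable over the four weeks before treatment, and ketogenic diet and VNS settings for three months before that period. This lowers the chance of new AED symptoms just before dosing.

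These points stand and limit the harm. They do not replace the same instrument before dosing: stable AED doses do not mean absent side effects, and the history listed in Section 5.5 does not name existing ones. Descriptive frequencies are also distorted if old symptoms are counted as new.

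Finally, the CRFs and the items of PESQ, QOLCE and Vineland are not part of the documents, so some other pre-dose symptom record may exist. That is correct.

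**Conclusion.** The point holds. A pre-dose PESQ is not assured under either reading of Section 7.2, and a site working from Sections 5.6 and 5.8 would not collect one. PESQ is listed at 9 of 10 clinic visits from Week 0, with the gap at the visit where dosing begins.

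The effect on adverse event counts is unknown. The documents give no background symptom rate, no PESQ items and no expected number of children at each dose. PESQ is one measure under the primary objective and is not the endpoint itself. The conclusion rests on the visit entries as written and does not claim that no pre-dose symptom record exists. It should be fixed, because the loss would be permanent and the remedy is small.

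**What to change.** Reconcile Sections 5.6, 5.8 and 7.2:

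- List PESQ at Week 0 in Sections 5.6 and 5.8, and state that the parent completes it before the first dose in clinic.
- At the same visit, record existing symptoms and their severity, so that new or worse can be judged against a written record.
- In Section 8.1, say that later PESQ responses, including the one at withdrawal, will be shown descriptively beside each child's pre-dose response. No formal change score is needed.

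The cost is a protocol amendment, one more parent questionnaire, a short symptom list and the related data entry at a visit already attended. Dosing, visits and sample size do not change.
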